#### **34. If a placebo group is used, include your justification**

N/A

#### **35. Criterios para el retiro prematuro del estudio**

- Manifest desire of the patient to withdraw from the protocol.
- What is not complying with the meal times that correspond to a patient's personal problem.
- Frequent hypoglycemias, genital infections, urinary tract infections, euglycemic ketoacidosis, anasopharyngitis and orthostatic hypotension that require hospitalization for the assessment and control of the patient's clinical condition.

#### **36. Procedures for the withdrawal of a patient from the study**

- Removal of data obtained through patient participation
- Valuation by medical specialists of the department.
- Assessment by department nutritionist.
- A conventional food plan is given.

#### **37. Criteria for premature suspension (partial or complete) of the study**

Undesirable side effects

#### **38. Selection criteria**

- a) Inclusion criteria (It must include the definition of the age groups, sex and the severity of the condition that will be allowed in the study)
  - a) Individuals with type 2 diabetes
  - b) Less than 10 years of evolution

c) Age between 40 and 70 years
 
d) Both genders.
 
e) With oral treatment scheme (oral hypoglycemic agents).
 
f) With HbA1c <9%
 
g) With BMI <math>\geq 25</math> to <math><40</math> kg / m^2

b) Exclusion criteria

a) Individuals with another type of diabetes.
 
b) Use of insulin.
 
c) Evolution time of more than 10 years.
 
d) Hospitalization in the last 3 months
 
e) Disease with poor short-term prognosis (for example: cancer)
 
f) Acute infection or febrile syndrome
 
g) Chronic disease other than those to be evaluated, for example: HIV, rheumatic diseases, liver cirrosis
 
h) Pregnancy
 
i) Who do not wish to participate in the study

c) Elimination criteria

a) Men or women who do not wish to continue in the study
 
b) Individuals who do not tolerate the placement of the MCGI
 
c) Individuals who are not attached to the meal plan.
 
d) Individuals who do not respect the corresponding meal times during the study.

39. Outcome and variables

a) Main variables / outcomes to be measured
 
BMI (kg / m^2)
 
a) Weight
 
Glycemic variability, defined with the following indices:
 
a) MAGE (mean amplitude of glycemic excursions)
 
b) MODD (mean of daily differences)
 
c) CONGA-n
 
b) Secondary outcomes to be measured:
 
a) Fasting glucose
 
b) Triglycerides
 
c) Total Cholesterol
 
d) HbA1c
 
e) Oxidative stress
 
f) FGF21
 
g) Systolic and diastolic BP
 
h) Hunger-Satiety Scale
 
a) Frequency of measurements:

Three measurements will be made in a 12-week period with a 6-week interval between each measurement, however the sensor placed in visit 2 will be left for 7 days during which glucose measurements in the interstitial fluid will be obtained every 5 minutes.

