## **11. Hypothesis**

1. 1. Weight loss in the TC3 group (Three meal times) will be more significant than in the TC6 group (Six meal times).
2. 2. It will significantly improve glycemic variability in patients undergoing the TC3 regimen.

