During the first visit, the clinical evaluation will be developed, which consists of a complete physical examination in which vital signs, neck and head examination, chest and abdomen examination, upper and lower limb examination will be measured. As well as a complete nutritional assessment that includes, anthropometric assessment by segments using dry label tape measure, dry brand pellotrometer and dry brand anthropometry; Body composition assessment using impedance OMRON model 512, 72hrs food consumption reminder to collect information on the feeding of each patient. Based on the information collected, the individualized TC6 plan will be prescribed and a 24/7 reminder format will be delivered to be filled out by the patient for a week, in addition to giving the indication to perform a blood glucose measurement at home once a day. in random scheme.			
To assess the adherence to the nutritional plan, the patient will be summoned 15 days later to perform daily			

consumption assessment using the 24/7 reminder format filled out by the patient and a 72hrs reminder made through an interview. Also, Hunger-Satiety levels will be measured with the Joslin institute tables validated for the Mexican population

If the patient adheres to the diet, blood samples will be taken to measure the variables (HbA1C, Glucose, Lipid Profile, Insulin, FGF-21) and after that place the continuous glucose monitor Medtronic model Ipro2 with in order to monitor the patient's blood glucose for 7 days.

At the end of 7 days, the patient will be summoned to remove the sensor and re-evaluate the diet.

The TC6 plan will be continued for 6 weeks, and at the end of this period the patient will be summoned again to perform blood samples to measure the variables (HbA1C, Glucose, Lipid Profile, Insulin, FGF-21), Weight, Blood pressure and hunger-satiety levels.

The TC6 regime will continue for another 6 weeks. At the end of the period, the patient will be cited to re-perform blood samples to measure the variables (HbA1C, Glucose, Lipid Profile, Insulin, FGF-21), Weight, Blood Pressure and Hunger-Satiety levels

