#### **42. Justification of the sample size (include the power of the study and the value of p that will be considered significant)**

For the calculation of the sample we consider (study on which we are based):

The calculation of the sample size was carried out taking as main outcome the body weight and considering the data of a study in which BMI and weight were evaluated. With these data considering a clinically significant difference, the sample size was calculated in 25 patients per group. A difference in weight 2kg, standard deviation of 2.5, alpha of 0.05 and power of 0.8 were used.

with the following formula:

$$n = 2S^2 (Z\alpha + Z\beta)^2$$

$$\Delta^2$$

Allowing to detect this difference with power of 80% (error  $\beta = 0.20$ ) and with an alpha error of 5%

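### Removing non-adherent patients' data, and fitting the glucose sensor only in adherent patients, opens the TC3 versus TC6 comparison to post-randomisation selection bias

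*Protocol*

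**What the plan says.** Four parts of the protocol act together.

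- **Section 38(c), elimination criteria.** Besides patients who no longer wish to take part, it eliminates those who do not tolerate the sensor, "Individuals who are not attached to the meal plan" and "Individuals who do not respect the corresponding meal times during the study".
- **Section 35, premature withdrawal.** One ground reads "What is not complying with the meal times that correspond to a patient's personal problem". The sentence is garbled, but it names non-compliance with meal times.
- **Section 36, withdrawal procedures.** The first item is "Removal of data obtained through patient participation".
- **Section 16, and the same text in the opening summary, for both arms.** The arm-specific plan is prescribed at the first visit and adherence is checked 15 days later. Then: "If the patient adheres to the diet, blood samples will be taken to measure the variables", after which the continuous glucose monitor is placed for 7 days.

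Section 39 lists weight and the variability indices MAGE, MODD and CONGA as main outcomes and describes one sensor period: "the sensor placed in visit 2 will be left for 7 days during which glucose measurements". Section 11 makes glycaemic variability the second hypothesis: "It will significantly improve glycemic variability in patients undergoing the TC3 regimen". Sections 27 and 42 justify 25 patients per group from weight alone.

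**The concern.** Randomisation makes the two groups comparable only as long as everyone randomised stays in the comparison. Here patients may leave it because of something that happens after assignment: whether they keep to the number of meals they were assigned. Keeping to three meals and keeping to six are different tasks, so the rule need not remove the same kind or number of patients from each arm. No adherence threshold is given, and section 13 describes only the information analyst as blinded, so the judgement may be made by staff who know the arm.

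If adherence is related to weight loss or glycaemia and elimination differs by arm, the remaining groups differ even when meal frequency has no effect. For glycaemic variability the problem goes further. The non-adherent patient's value is never measured, so the adherent-only comparison is the only one possible.

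**Working it through.** **1. Which data are lost, and by which route**

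| Outcome | Lost through the day-15 adherence condition | Lost through elimination and data removal |
|---|---|---|
| MAGE, MODD, CONGA | Yes; the visit-2 sensor is the only one described | Yes |
| Visit-2 HbA1c, glucose, lipids, insulin, FGF21 | Yes | Yes |
| Later blood samples | No | Yes |
| Weight | No | Yes |

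The time of randomisation is not stated outright. The arm-specific plan is prescribed at the first visit, however, so assignment precedes the adherence check.

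**2. The plan's own sample size**

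Inputs from sections 27 and 42: difference 2 kg, SD 2.5 kg, alpha 0.05 (two-sided reproduces the figure), power 0.80.

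n = 2 × 2.5² × (1.96 + 0.84)² / 2² = 12.5 × 7.84 / 4 = 24.5, rounded up to 25 per group. The figure is correct. It has no margin for the eliminations that section 38(c) prescribes.

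Power by the same formula is Φ(2 / (2.5 × √(2/n)) − 1.96):

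| Analysed per group | Formula | Exact t-test |
|---|---|---|
| 25 | 80.7% | 79.1% |
| 24 | 79.1% | 77.4% |
| 22 | 75.6% | 73.6% |
| 20 | 71.6% | 69.3% |

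One loss per arm is immaterial. Five per arm cost about 9 points.

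**3. Illustration of the bias (all inputs assumed except the SD)**

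The protocol gives no elimination rates and no link between adherence and outcome. Assume no true effect, SD 2.5 kg, the least adherent removed, and correlation ρ between latent adherence and outcome. With p₁ and p₀ the proportions eliminated in the two arms, φ the normal density and z the matching quantile:

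bias in SD units = ρ × [φ(z_p₁)/(1 − p₁) − φ(z_p₀)/(1 − p₀)]

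- For 30% versus 10%: 0.3477/0.7 − 0.1755/0.9 = 0.4967 − 0.1950 = 0.3017.
- For 20% versus 10%: 0.2800/0.8 − 0.1950 = 0.3500 − 0.1950 = 0.1550.

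Multiplying by ρ and by 2.5 kg gives the false difference. Type I error was simulated with 25 per arm before elimination, a pooled t-test and a fixed adherence threshold (100,000 runs).

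| Eliminated | False difference, ρ = 0.3 / 0.5 / 0.7 | Type I error |
|---|---|---|
| 30% vs 10% | 0.23 / 0.38 / 0.53 kg | 5.8 / 7.6 / 10.8% |
| 20% vs 10% | 0.12 / 0.19 / 0.27 kg | 5.3 / 5.6 / 6.6% |
| 20% vs 20%, same threshold | about 0 kg | 5.0 / 5.1 / 5.0% |

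If exactly 7 and 2 of 25 are removed instead (200,000 runs), type I error is 6.1 / 8.4 / 12.4%. For glycaemic variability the protocol gives no SD; the 30% versus 10% case equals 0.09 / 0.15 / 0.21 SD of whichever index is used.

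**The case against.** **The link from non-adherence to data removal is inferred.** Section 36 is one terse item and does not say who triggers removal or which data it covers; it might mean deletion when a patient revokes participation. Section 38(c) does not mention data, and the bridge through section 35 is a garbled sentence. This has some force: the sections permit deletion for non-adherence rather than spelling it out. Removal of the withdrawn patient's study data is still the plainest reading.

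**The adherence condition is incomplete.** The protocol does not say what happens when the patient does not adhere. Sections 30 and 39 promise three samplings without any adherence condition, and the later blood samples and weights are unconditional. This stands for those outcomes. It does not help glycaemic variability, because no other route to a sensor is described.

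**The analysis population belongs in an analysis plan that is not at hand.** That is right as far as naming the population goes. No later plan, however, can analyse values that were deleted or never measured.

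**Sensor intolerance is not adherence to the diet.** This is true, and the documents give no reason to expect it to differ by arm. It is equally no reason to discard such a patient's weight.

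**The illustrated bias is modest and rests on assumed inputs.** Also true: against the 2 kg design difference, 20% versus 10% gives at most 0.27 kg and 6.6%. The case rests on the loss being irreversible, not on these figures.

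**Conclusion.** The concern holds. As written, the protocol leaves non-adherent patients without any measurement of a main outcome, and it permits deletion of their other outcomes because of adherence to the randomised factor itself. The comparison is therefore open to selection bias whose size and direction cannot be known from the documents, and could not be checked once the data are gone. The illustrated range runs from none (equal elimination by the same threshold) to 0.53 kg with type I error of 10.8% (12.4% with exact counts), and depends wholly on assumed elimination rates and correlations. The sample size of 25 per group is not in dispute. The loss of power from eliminations is secondary. This needs correcting in the protocol before data are lost.

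**What to change.** 1. State that all randomised patients are analysed in the assigned group, whatever their adherence.
2. Remove elimination criteria (b), (c) and (d) of section 38(c) as reasons for excluding data. This concerns the data only, not whether a patient stops the diet.
3. Replace the data-removal item in section 36 with a rule that data collected up to withdrawal are kept unless the patient asks for deletion. Rewrite the garbled ground in section 35 so that its meaning is clear.
4. In section 16 and the summary, take the day-15 samples and offer the sensor to every patient regardless of the adherence check, and keep measuring weight at the scheduled visits.
5. Report the adherent-only comparison as a labelled sensitivity analysis, with eliminations and reasons by arm.
6. Optionally, say in sections 27 and 42 that the claim "Allowing to detect this difference with power of 80"% assumes 25 analysed per group, and give the power at plausible losses from the table above.

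**Cost.** Extra sensors, assays and visits for non-adherent patients already among the 50; an amendment to the two committees named in section 45; and possibly a change to the consent wording on data removal. The estimated effect may also be smaller. If, by assumption, 20% of patients gained nothing from the assigned plan and 2 kg is the effect in the rest, the average effect is 0.8 × 2 = 1.6 kg and formula power with 25 per group is Φ(1.6/0.707 − 1.96) = 61.9%. That is the price of estimating the effect of assigning the diet, and it should be accepted knowingly.

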## **26. Failure and success criteria**

Success: Corroborate that the effects of a TC3 diet are more beneficial than a conventional TC6 plan. To achieve this, patients should have better glycemic variability, lose more weight, improve fasting blood glucose, improve HbA1c, optimize their lipid level, improve oxidative stress markers and have better control of Hunger-Satiety.

Failure: That the effects of a TC3 diet be equal or less beneficial to the patient's health than a conventional TC6 plan.

**27. Sample size (please include the formula used for the calculation and the source of information on which the assumptions were based)**

a) Sample size

The calculation of the sample size was carried out taking as main outcome the body weight and considering the data of a study in which BMI and weight were evaluated. With these data considering a clinically significant difference, the sample size was calculated in 25 patients per group. A difference in weight 2kg, standard deviation of 2.5, alpha of 0.05 and power of 0.8 were used.

with the following formula:

$$n = 2S^2 (Z\alpha + Z\beta)^2$$

$$\Delta^2$$

Allowing to detect this difference with power of 80% (error  $\beta = 0.20$ ) and with an alpha error of 5%

**28. Description of the techniques, devices and / or instruments that will be used in the measurement (Including: special mechanical, electronic, cybernetic equipment)**

An RJL body composition analyzer with stadiometer will be used.

An ergonomic continuous fiberglass tape measure will be used to measure the circumference of the Seca201® brand body

For the continuous measurement of glucose and glycemic variability, the Medtronic Ipro2 Sensor will be used.

The blood samples will be labeled prior to their inclusion in the "Beckman GPKR Centrifuge" equipment to perform their centrifugation and to be able to separate serum samples, to obtain the laboratories and eppendorf containers will be stored, for each time, to be able to consult later before any situation of doubt Samples will be separated from the tubes to obtain the laboratories.

Beckman-Coulter equipment will be used for the analysis of samples corresponding to blood count.

The Hunger-Satiety scales of the Joslin Institute will be used.

Computing teams of the Department of Endocrinology will be occupied, which have Windows 8.1 pro operating system.

The Easy GV® Software will be used to calculate the glycemic variability indices.

SPSS V21 will be used for data capture and analysis.

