#### **41. Statistical analysis (Description of the processing plan and presentation of the information. Include the justification of the statistical tests that will be used)**

The distribution of the variables will be evaluated with the Shapiro-Wilk test. Descriptive statistics will be used for the presentation of the variables, estimating averages and standard deviation for variables with normal and median distribution and interquartile range for variables with non-normal distribution. The prevalence and frequencies will be expressed in terms of percentage. The variables in each group will be compared by Student's T-test or U-Mann Whitney (as appropriate). Categorical variables will be compared by Fisher's exact test or Chi square analysis. A statistically significant difference with a value of  $P < 0.05$  will be considered. The statistical program SPSS version 21 will be used for data analysis.

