#### **43. Recruitment potential (number of subjects to be recruited)**

25 subjects for a diet in 3 meal times.

25 subjects for a diet in 6 meal times.

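### The protocol disagrees with itself on its main outcome, and testing five unranked main outcomes each at P < 0.05 gives more than a 5% chance of at least one false main result if any one of them may be claimed

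*Protocol*

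**What the plan says.** - **Sections 27 and 42 (sample size).** "The calculation of the sample size was carried out taking as main outcome the body weight". The inputs are given as "A difference in weight 2kg, standard deviation of 2.5, alpha of 0.05 and power of 0.8 were used", and "the sample size was calculated in 25 patients per group". No other outcome is sized.
- **Section 11 (hypotheses) and section 12 (primary objective).** There is one hypothesis for weight loss and one for glycemic variability. The primary objective compares the regimens on both together.
- **Section 39 a (main variables).** BMI and weight are listed, followed by "Glycemic variability, defined with the following indices": MAGE, MODD and CONGA-n. None is ranked above another, and n in CONGA-n is left open.
- **Section 41 (statistical analysis).** The variables are compared between groups by t-test or Mann-Whitney. "A statistically significant difference with a value of" P < 0.05 is the only threshold, and it applies to every variable.
- **Section 26 (success and failure).** Success is a list of improvements: glycemic variability, weight, fasting glucose, HbA1c, lipids, oxidative stress markers and hunger-satiety. Failure is TC3 being equal to or less beneficial than TC6. No statistical rule is attached.

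**The concern.** A reader of sections 27 and 42 would take weight as the one main outcome. A reader of section 12 would take two, and a reader of section 39 would take five. Section 41 does not settle the matter, because it gives all of them the same unadjusted threshold.

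Two things are at stake. First, if a significant result on any one of the five may be presented as a positive main finding, the chance that a trial of two equivalent regimens yields such a finding is well above the 5% used for each test. Second, only weight has a power justification, so a main claim on a glucose index would rest on a comparison that the trial was not sized for.

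**Working it through.** **Inputs from the protocol.** Difference 2 kg, SD 2.5 kg, alpha 0.05, power 0.80, 25 per group (sections 27 and 42); five main outcomes (section 39); P < 0.05 per comparison (section 41).

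**Step 1: reproduce the plan's own figure.** The stated formula is n = 2S²(Zα + Zβ)²/Δ². With two-sided alpha 0.05:

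n = 2 × 2.5² × (1.960 + 0.842)² / 2² = 24.5, rounded up to 25 per group.

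This matches. A one-sided alpha would give 20, so the calculation is two-sided. Power at 25 per group is 80.7% by the normal approximation and 79.1% by the t-test. The sample size is therefore a calculation for weight alone with the whole 0.05 spent on it.

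**Step 2: chance of at least one false positive among k independent tests at 0.05, which is 1 − 0.95^k.**

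| Tests | Reading | Result |
|---|---|---|
| 1 | weight only | 5.0% |
| 2 | weight and one glucose index | 9.75% |
| 4 | weight and three indices | 18.5% |
| 5 | all listed in section 39 | 22.6% |

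**Step 3: allow for correlation.** The five are related: BMI and weight closely, and the three indices because they come from the same sensor record. The protocol gives no correlations, so these are assumptions. Five two-sided z tests were simulated with no true difference, with 400,000 or more draws per setting.

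| Weight-BMI | Between indices | Between the two sets | At least one of five |
|---|---|---|---|
| 0.80 | 0.5 | 0 to 0.2 | 19.1-19.3% |
| 0.95 | 0.5 | 0 to 0.2 | 18.0-18.2% |
| 0.95 | 0.9 | 0 to 0.2 | 14.1-14.2% |
| 0.99 | 0.9 | 0 to 0.2 | 13.4-13.5% |

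The limits are 5% if all five were the same test and 22.6% if all were independent. For weight plus one index, cross-correlations up to 0.2 leave the figure at about 9.6-9.8%.

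**Step 4: a joint rule, for contrast.** Suppose a claim needs a significant body-size result and at least one significant glucose index. With weight-BMI correlation 0.95-0.98, index correlations 0.5-0.9 and cross-correlation 0.1-0.2, false success falls to about 0.7-0.9%.

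**Step 5: cost of splitting alpha, for weight at 25 per group.**

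| Alpha for weight | Power, t-test | Power, normal | n per group for 80% (normal) |
|---|---|---|---|
| 0.05 | 79.1% | 80.7% | 25 |
| 0.025 | 69.6% | 72.1% | 30 |
| 0.01 (0.05/5) | 56.2% | 60.0% | 37 |

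**The case against.** **Section 26 is not an any-one rule.** This is the strongest objection, and it stands as far as it goes. Read literally, section 26 asks for improvement across a list, and under such a rule a false overall success would be rarer than 5% (step 4), with low power becoming the problem instead. A reader might infer that the protocol lets any single one of the five win the trial. The text does not say so. But section 26 names no test and does not say which of three indices represents glycemic variability. It also does not govern when an individual main comparison is called significant; section 41 does. The error rates above therefore apply only to claiming at least one main result under section 41.

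**The protocol promises no family-wise 5%.** Correct. Its 5% is the alpha of the weight calculation and the per-test threshold. A reader should not conclude that a stated overall error rate has been breached.

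**The 14-19% rests on assumptions.** Also correct. BMI is weight over a constant within a patient but not between patients of different height, so a near-perfect correlation is not assured. That is why a setting of 0.80 is included.

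**The list may hold fewer than five outcomes.** The layout could be read with BMI as a heading over weight. Four outcomes remain, and under the same index correlations (0.5-0.9) the rate is about 13-17%. The point is unchanged.

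**One could multiply across all 14 main and secondary measures, giving 1 − 0.95^14 = 51%.** That treats plainly related variables as independent and counts secondary outcomes for which no confirmatory claim is made. It should not be used.

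**A separate analysis plan could add an order among outcomes.** It could, and the absence of such detail alone would not be a finding. But it would first have to choose between sections of the protocol that disagree.

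**Conclusion.** The protocol contradicts itself on its main outcome: one in sections 27 and 42, two in section 12, five in section 39, with a single unadjusted threshold for all in section 41. If any one main outcome may be reported as a positive main result, the chance of at least one false result is about 10% for weight plus one glucose index, roughly 14-19% for all five under the assumed correlations, and 22.6% if they are independent. These figures count one comparison per outcome. Section 39 plans three measurements without naming a primary time point and leaves n in CONGA-n open, so further choices could raise them.

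The sample size is not wrong: 25 per group reproduces for weight at two-sided 0.05. Severity: should be fixed, because the choice has to be made before the data are seen and making it costs little.

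**What to change.** Make sections 12, 27, 39, 41 and 42 agree:

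1. Name weight change at the final visit as the single primary outcome, tested at two-sided 0.05.
2. Name one glycemic variability index before unblinding (for example MAGE) as the next outcome in a prespecified sequence, tested at 0.05 only if weight is significant.
3. Report BMI, the other indices (with n in CONGA-n fixed) and the secondary outcomes as supportive, with 95% confidence intervals and no confirmatory claim.
4. State in section 26 how its success list relates to this primary test.

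**Cost.** Protocol wording only. Weight keeps the full 0.05, so 25 per group stands. The downside is that glycemic variability cannot be claimed as confirmatory if weight fails, although section 12 names it jointly with weight.

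Weight first and MAGE second is one acceptable order, not the only one; the documents do not rank MAGE above MODD or CONGA. The sponsor may choose another prespecified scheme that controls the error rate, but should then state its effect on power for weight. An equal split of 0.025 each between weight and one glucose index, for example, leaves about 70% power for weight by the t-test at 25 per group.
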